2.3.1 Efficacy populations

Efficacy analyses will be based on the treatment group allocated by the IRT according to the randomization schedule at randomization visit (as randomized), irrespective of the treatment actually received.

2.3.1.1 ITT population

Efficacy analyses will be based on the ITT population, defined as all randomized patients, irrespective of compliance with the study protocol and procedures. Patients will be analyzed for efficacy according to the treatment group to which they are randomized.

2.3.1.2 ABPM substudy population

ABPM efficacy analysis will be based on ABPM substudy population which defined as all randomized patients having:

1. signed the informed consent for ABPM substudy
2. Eligible screening SBP ≥ 130 mmHg
3. Baseline ABPM measurement at Visit 3A with Good Quality (see Appendix D)
4. At least one post-baseline ABPM visit recording.

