11.3 ANALYSIS POPULATIONS

11.3.1 Efficacy populations

Efficacy analyses will be based on the treatment group allocated by the IRT according to the randomization schedule at randomization visit (as randomized), irrespective of the treatment actually received.

11.3.1.1 *Intent-to-treat population*

Efficacy analyses will be based on the ITT population, defined as all randomized patients, irrespective of compliance with the study protocol and procedures. Patients will be analyzed for efficacy analyses according to the treatment group to which they are randomized.

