11.4.2.4 Analysis of ambulatory blood pressure monitoring substudy endpoints

ABPM substudy endpoints will be analyzed using a similar approach as the primary efficacy endpoint with missing values imputed by control-based multiple imputation method under the missing not at random frame work. Each of the complete dataset will be analyzed using ANCOVA model including factors for treatment (sotagliflozin, placebo), randomization stratum of HbA1c ($\leq 8.0\%$, $>8.0\%$) as fixed effects, and the baseline value of the specific dependent variable as a covariate.

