The randomization strata [HbA1c at Screening ($\leq 8.0\%$, $>8.0\%$) and mean SBP (<130 , ≥ 130 mmHg)] assigned by IRT will be summarized. The percentages will be calculated using the number of randomized patients as the denominator. The discrepancy between the strata assigned by IRT and the information reported on eCRF will be listed for all randomized patients.

Kaplan-Meier (KM) plots of the cumulative incidence of double-blind IMP discontinuation due to any reason and due to AE will be provided for the entire 79-week double-blind treatment period separately (see [Section 2.5.4](#)). A listing of these patients, along with the reason for discontinuation treatment, study completion status and the reason for discontinuation study, will be provided.

For ABPM sub-study, the number of patients in each of the following categories will be summarized.

- Patients who consented to ABPM substudy
- Patients not entering ABPM substudy and the reason for not entering
- Patients who randomized and entered ABPM substudy (ie, ABPM substudy population, see [Section 2.3.1.2](#))
- Patients who completed ABPM substudy
- Patients who discontinued ABPM substudy and the reason for discontinuation:
 - Adverse Event
 - Study Terminated by Sponsor
 - At patient's own request
 - Lost to follow-up
 - Poor compliance to Protocol
 - Other
- Patients with good quality (see Appendix C) ABPM measurements at either Visit 7A/Week 12, or Visit 9A/Week 26 or both visits.

For patients who consented but did not enter ABPM substudy, percentages will be calculated using the number of patients consented to substudy as the denominator. All other categories of patients will be presented by treatment group and the percentages will be calculated using the number of patients randomized and entered substudy within each treatment group as the denominator. Reasons for ABPM substudy discontinuation will be supplied in tables giving numbers and percentages by treatment group. Patients prematurely discontinued the substudy, along with reasons for discontinuation, will also be listed. Patients who consented but did not enter ABPM substudy, along with reasons for not entering, will also be presented.

All important deviations including randomization and drug-dispensing irregularities will be summarized in tables giving numbers and percentages of deviations by randomized treatment group.

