2.4.4.1 Analysis of primary efficacy endpoint(s)

The statistical test will be two-sided at a nominal 5% significance level.

Primary analysis

The primary efficacy endpoint change in HbA1c from baseline to Week 26 will be analyzed by an ANCOVA model using HbA1c values measured at baseline and Week 26 (observed or imputed). The missing data at endpoint will be imputed by multiple imputation (MI) methods in 2 parts as detailed below. To be concise, the following texts related to imputation are generalized to accommodate primary as well as continuous secondary efficacy endpoints.

1. Missing endpoint data for patients who prematurely discontinue the IMP before the Week 26 (or Week 12 for SBP) visit will be imputed using a model built separately in each treatment group and estimated from the patients in the same treatment group who prematurely discontinue the IMP before the Week 26 (or Week 12 for SBP) visit but have

the measurement for the endpoint (retrieved dropouts). Considering that the number of patients in each treatment group who discontinue the IMP but have the measurement for the endpoint is expected to be small, a simple imputation model based on regression will be used with baseline measurement included as the predictor. Each treatment group will have their own imputation model.

2. Missing endpoint data for all patients who stay on the IMP until the Week 26 (or Week 12 for SBP) visit, including those in the sotagliflozin 400 mg group, will be imputed separately. The wash-out imputation method will be used, where missing endpoint data in the sotagliflozin 400 mg group, as well as in the placebo group are imputed from a model estimated from patients in the placebo group who stay on the IMP until the Week 26 (or Week 12 for SBP) visit and have the endpoint data available. The imputation model will include the randomization strata and the corresponding baseline value. Missing data will be imputed using the regression method.

An alternative (back-up) imputation method will be used if the number of patients who prematurely discontinue the IMP before the Week 26 (or Week 12 for SBP) visit but have the measurement for the endpoint is <5 in any treatment groups (ie, not sufficient retrieved dropouts to support the imputation method described above). This criterion will be assessed for each primary or continuous secondary efficacy endpoint separately.

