2.4.4.4 Analysis of ABPM substudy efficacy endpoints

Analyses of ABPM substudy efficacy endpoints will be performed on the ABPM population using all assessment collected up to Week 26, including those obtained after IMP discontinuation or introduction of rescue therapy, unless otherwise specified.

For ABPM substudy, primary and secondary efficacy endpoints will be analyzed using a similar approach as in the main-study with post-baseline missing values imputed by the retrieved dropouts & washout imputation method or by the control-based copy reference imputation method according to the criterion described in [Section 2.4.4.1](#). Each of the complete dataset will be analyzed using ANCOVA model including factors for treatment (sotagliflozin 400 mg, placebo), randomization stratum of HbA1c ($\leq 8.0\%$, $> 8.0\%$) as fixed factor, and the baseline value of the specific dependent variable as a covariate. Results from each complete dataset will be combined using Rubin's formula to provide the adjusted mean for each treatment group, as well as the between-group difference and the associated 95% CI.

All ABPM substudy efficacy endpoints will also be summarized by descriptive statistics by scheduled visits (Visit 3/Randomization, Visit 7/Week 12 and Visit 9/Week 26). The descriptive statistics will include number, mean, SE, standard deviation, minimum, maximum.

Please refer to Appendix C and Appendix D for ABPM substudy efficacy variable derivation.

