2.4.4.5 Multiplicity issues

To control the family-wise type I error, a fixed-sequence testing procedure will be applied.

Once the primary variable (Change from Baseline to Week 26 in HbA1c) is statistically significant at $\alpha = 0.05$ (2-sided), the following main secondary efficacy variables and ABPM substudy primary endpoint will be tested in the following prioritized order. The testing will stop as soon as an endpoint is found not to be statistically significant at $\alpha=0.05$ (2-sided).

- Change from Baseline to Week 26 in 2-hour PPG following an MM
- Change from Baseline to Week 26 in FPG
- Change from Baseline to Week 26 in body weight
- Change from Baseline to Week 12 in SBP for patients with baseline SBP ≥ 130 mmHg
- Change from Baseline to Week 12 in SBP for all patients
- Change from Baseline to Week 12 in average 24-hour SBP in patients from ABPM substudy (the primary endpoint of the ABPM substudy)
- Proportion of patients with HbA1c $< 7.0\%$ at Week 26.

No multiplicity adjustment will be made on efficacy variables other than those mentioned above.

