2. Visit Recording has less than 44 total measurements.

A valid measurement is a measurement having non-missing values for systolic, diastolic, pulse pressure and mean arterial pressure (MAP). [REDACTED] will analyze the recording from the first valid inflation (after device initiated) up to 24 hours thereafter to determine the quality of the recording. If the quality of the visit recording is of Not Good Quality, the efficacy variable of the patient at that visit will be considered as missing value. Otherwise, the efficacy variable of the patient at the visit will be calculated as follow:

Statistical Analysis Plan**Version: 3**

Lexicon Pharmaceuticals Protocol No. EFC14834

Date of Issue: 10 December 2019

Covance Study ID: 000000150525

Summing over all successful included systolic/diastolic measurements collected during the time interval (24-hour, actigraphy reported sleep time or actigraphy reported wake time), then divide the total by number of successful included measurements.

The actigraphy can detect the patient's sleep or wake time based on the patient's activity intensity. If the patient has interruptive sleep periods, the actigraphy will report the first inactivity period of the patient as the patient's sleep time. Wake time will be the time outside the sleep interval. Each patient will only have one sleep time and one wake time reported by the device.

Statistical Analysis Plan**Version: 3**

Lexicon Pharmaceuticals Protocol No. EFC14834

Date of Issue: 10 December 2019

Covance Study ID: 000000150525

Appendix E Potentially clinically significant abnormalities criteria**CRITERIA for POTENTIALLY CLINICALLY SIGNIFICANT ABNORMALITIES
for phase 2/3 studies (oncology excepted)**

Parameter	PCSA	Comments
Clinical Chemistry		
ALT	By distribution analysis : >3 ULN >5 ULN >10 ULN >20 ULN	Enzymes activities must be expressed in ULN, not in IU/L. Concept paper on DILI – Food and Drug Administration (FDA) draft Guidance Oct 2007. Internal DILI WG Oct 2008. Categories are cumulative. First row is mandatory. Rows following one mentioning zero can be deleted.
AST	By distribution analysis : >3 ULN >5 ULN >10 ULN >20 ULN	Enzymes activities must be expressed in ULN, not in IU/L. Concept paper on DILI – FDA draft Guidance Oct 2007. Internal DILI WG Oct 2008. Categories are cumulative. First row is mandatory. Rows following one mentioning zero can be deleted.

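### The ABPM analysis set requires a post-baseline recording, so substudy patients with none at either Week 12 or Week 26 are dropped from an alpha-controlled test instead of being imputed

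*SAP*

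**What the plan says.** SAP 2.3.1.2 defines the ABPM substudy population by four criteria: substudy consent, eligible screening SBP of at least 130 mmHg, a good-quality baseline recording at Visit 3A, and "At least one post-baseline ABPM visit recording". SAP 2.4.4.4 runs the ABPM analyses on that population, with "post-baseline missing values imputed by the retrieved dropouts & washout imputation method" or by the control-based back-up.

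The protocol defines no narrower ABPM set. Its general rule (11.3.1.1) is that "Efficacy analyses will be based on the ITT population, defined as all randomized patients, irrespective of compliance with the study protocol and procedures". For the substudy, 11.4.2.4 states that "ABPM substudy endpoints will be analyzed using a similar approach as the primary efficacy endpoint with missing values imputed by control-based multiple imputation method", and Appendix B repeats this.

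Three other places in the SAP matter:

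- **2.4.4.5** places "Change from Baseline to Week 12 in average 24-hour SBP in patients from ABPM substudy (the primary endpoint of the ABPM substudy") sixth among the seven endpoints tested after the primary, immediately before HbA1c <7.0%.
- **Appendix D** says that when a visit recording is not of good quality, "the efficacy variable of the patient at that visit will be considered as missing value".
- **2.2** describes the same population as patients randomized and entered into the substudy, while pointing back to 2.3.1.2.

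**The concern.** The first three criteria rest on information fixed before randomization, so a set built on them keeps the randomized comparison within the substudy. The fourth depends on what happens afterwards. Once patients are selected on a post-randomization event that treatment can influence, the arms being compared are no longer the randomized substudy groups.

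The patients removed are mainly those who leave before the Week-12 ABPM window opens (Day 70, SAP 2.5.4). They are the natural targets of the missing-not-at-random imputation, yet criterion 4 stops them from reaching it. If removed sotagliflozin patients would have responded less than those recorded, the restricted set overstates the effect.

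The test is under family-wise error control and decides whether HbA1c <7.0% may be tested. Appendix G lists no supportive analysis for this endpoint, and the additional ABPM imputation analysis in SAP 1.6 names no wider population. No planned analysis would therefore show what the exclusion did.

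**Working it through.** **Who is removed.** Only patients with no recording at both post-baseline visits.

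| Patient with a valid baseline recording | SAP handling |
|---|---|
| Stopped IMP but was recorded | Kept, value used |
| Recorded at Week 26, not at Week 12 | Kept, Week 12 imputed |
| Only post-baseline recording unusable | Kept, set to missing, imputed |
| No post-baseline recording | Removed |

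The last two rows carry the same usable post-baseline information, namely none, but are treated differently.

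**Whether imputation needs criterion 4.** It does not. The retrieved-dropout model in SAP 2.4.4.1 uses the baseline value alone. The washout model uses baseline and strata. The copy-reference back-up can also run from these. Criterion 3 guarantees the baseline value.

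**The plan's own figure.** Inputs (Protocol 11.1, SAP 1.3): 100 per arm, difference 7 mmHg, SD 15 mmHg, two-sided 0.05. The noncentrality is 7 / (15 × √(2/100)) = 3.30; with 198 degrees of freedom the power is 90.7%. The stated 90% is reproduced.

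**Effect of the choice.** Assumptions not in the documents: a share *m* of each arm has no post-baseline recording, equal in both arms; 7 mmHg is the effect among recorded patients; removed sotagliflozin patients keep a share *r* of it; the placebo mean is unchanged.

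- Exclusion: effect 7, n = 100(1 − *m*) per arm.
- All entrants, imputed: effect = 7(1 − *m*) + 7*rm*, n = 100 per arm.

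*r* = 0 corresponds to placebo-level imputation (washout or copy reference). Under own-arm retrieved-dropout imputation *r* may lie between 0 and 1, because missing values "will be imputed using a model built separately in each treatment group and estimated from the patients in the same treatment group" who stopped IMP but were measured.

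| *m* | Effect, *r* = 0 | *r* = 0.5 | *r* = 1 | Overstatement by the restricted set (*r* = 0 / 0.5 / 1) |
|---|---|---|---|---|
| 1% | 6.93 | 6.97 | 7.00 | 1.0% / 0.5% / 0% |
| 3% | 6.79 | 6.90 | 7.00 | 3.1% / 1.5% / 0% |
| 5% | 6.65 | 6.83 | 7.00 | 5.3% / 2.6% / 0% |
| 10% | 6.30 | 6.65 | 7.00 | 11.1% / 5.3% / 0% |

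Overstatement is 7 divided by the all-entrant effect, minus 1; for example 7/6.30 − 1 = 11.1%.

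| *m* | Power, exclusion | Power, imputed at *r* = 0 | Gap (points) |
|---|---|---|---|
| 1% | 90.4% (n = 99) | 90.2% | 0.3 |
| 3% | 89.9% (n = 97) | 89.0% | 0.9 |
| 5% | 89.2% (n = 95) | 87.7% | 1.6 |
| 10% | 87.6% (n = 90) | 84.0% | 3.5 |

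Gaps are taken before rounding. The imputed powers treat imputed values as observed, so they are upper bounds.

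**Type I error.** The model above gives no bias under the null, since *r* then multiplies a zero effect. Inflation needs unequal loss and a different prognosis in those lost. For illustration (invented inputs), take 15% loss on sotagliflozin, 5% on placebo, and lost patients 10 mmHg worse than those kept. The difference shifts by (0.15 − 0.05) × 10 = 1.0 mmHg in favour of sotagliflozin. With SE = 15 × √(1/85 + 1/95) = 2.24, the two-sided error is about 7.3%. At 10% versus 5% it is 5.6%; with equal loss it stays at 5.0%.

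**The case against.** The case on the other side is mostly about size, and much of it stands.

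- **The relevant loss may be low.** It is the share with no recording at either visit, not substudy dropout. Patients who stop IMP are encouraged to complete the substudy (Protocol 10.3.3), inadequate recordings are repeated (Protocol 9.5), a poor recording still satisfies criterion 4, and the windows are wide and contiguous (Days 70–133 and 134–227). Nothing in the documents makes 5% a floor, which is why the tables also show 1% and 3%.
- **The direction is not certain.** Under own-arm retrieved-dropout imputation the placebo mean can move too, since any treatment other than an SGLT2 inhibitor is allowed after IMP is stopped. The calculation holds that mean fixed and cannot show a shift the other way. Calling the restricted estimate too large at *r* = 0 also takes placebo-level imputation as the target.
- **Inflation of type I error is possible, not demonstrated.** The 7.3% rests on two invented inputs acting together.
- **The protocol's ITT wording cannot apply literally to a subset.** A substudy needs its own set. Criteria 1 to 3 supply it from pre-randomization information, and the protocol's explicit instruction to impute missing ABPM values leaves no role for criterion 4.
- **The disposition point depends on the reading.** SAP 2.2 can be read as counting every entrant. Taken literally, its cross-reference leaves these patients out of the denominators, and no listed row counts them by arm.

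None of this supplies a reason to keep the condition.

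**Conclusion.** The concern holds. A post-randomization condition governs entry to an alpha-controlled analysis, it departs from the protocol's rule of analysing randomized patients and imputing missing ABPM values, and it treats patients with equivalent missing information differently. Only the ABPM test and, through the gate, HbA1c <7.0% are exposed; the latter's own ITT analysis is unchanged.

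The size cannot be fixed from the documents. With equal assumed loss of 5% to 10% per arm and placebo-level outcomes in those lost, the overstatement is 5.3% to 11.1% and the exclusion gains about 1.6 to 3.5 points of power. At 1% loss the figures are 1.0% and 0.3 points, and there is no overstatement if lost patients keep the full effect. It should be fixed: the consequence is of unknown size and the condition serves no technical purpose.

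**What to change.** 1. Delete criterion 4 from SAP 2.3.1.2. The set becomes all randomized patients with ABPM consent, screening SBP of at least 130 mmHg and a good-quality Visit 3A recording.
2. Impute missing Week 12 and Week 26 values by the scheme already given in SAP 2.4.4.1 and 2.4.4.4.
3. Keep the current set as a supportive analysis and list it in Appendix G.
4. Align the population wording in SAP 2.2, 2.3.1.2 and 2.4.4.4, and add a disposition row giving, by arm, the number of substudy patients with no post-baseline recording.

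The cost is a line removed, a label aligned, and a disposition row and a supportive analysis added; no new data are needed. The downside is an ABPM estimate that may be somewhat smaller and slightly less precise.

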2.3.2 Safety population

Safety analyses will be based on the safety population, defined as all randomized patients who receive at least one dose of double-blind IMP (regardless of the amount of treatment administered). Patients will be analyzed according to the treatment actually received.

In addition:

- Nonrandomized but treated patients will not be part of the safety population; however, their safety data will be presented separately
- Randomized patients for whom it is unclear whether they took the IMP will be included in the safety population as randomized
- When a patient is exposed to both sotagliflozin and placebo, the patient will be analyzed in the sotagliflozin group
- Randomized patients will be excluded from the safety population only if there is documented evidence (ie, all study dates recorded as no medication taken) that patients have not taken the study treatment. If a patient is dispensed double-blind IMP and is lost to follow-up without any documented evidence, the patient will be considered exposed.

2.3.3 PK population

For PK analyses, the PK population is defined as all safety patients who contribute with at least 1 valid plasma concentration of sotagliflozin or its 3-O-glucuronide metabolite. PK data will be analyzed according to the treatment actually received.

2.4 STATISTICAL METHODS

Descriptive statistics (number, mean, standard deviation (SD), median, minimum, and maximum) will be presented for continuous variable by treatment group. The number and percentage of patients in each category will be presented for categorical variables by treatment group.

2.4.1 Demographics and baseline characteristics

Parameters will be summarized in the randomized population analyzed in the treatment group to which they were randomized. Analyses for the safety population will be included in the appendices if the size of the safety population is different (>10%) from the size of that in the primary analysis population for any treatment group.

Parameters described in [Section 2.1.1](#) will be summarized by treatment group and overall (pooled across treatment groups) groups using descriptive statistics.

Demographic and disease characteristics will be summarized for ABPM substudy population by treatment group and overall (pooled across treatment groups) groups using descriptive statistics.

P-values on the treatment difference for demographic and baseline characteristic data will not be calculated.

In general, no specific description of the safety parameters will be provided at baseline. If relevant, the baseline values will be described along with each safety analysis.

In general, no specific description of the efficacy parameters will be provided at baseline. If relevant, the baseline values will be described along with each efficacy analysis.

2.4.2 Prior or concomitant medications

The prior, concomitant and posttreatment medications will be presented in the randomized population for each treatment group (and overall for the summary of prior medications), using counts and percentages. No statistical test for the between-group difference will be performed.

Medications will be summarized by treatment group according to the WHO-DD dictionary, considering the first digit of the Anatomical Therapeutic Chemical (ATC) class (anatomic category) and the first 3 digits of the ATC class (therapeutic category). A given medication may be classified in more than 1 ATC class. All ATC codes corresponding to a medication will be summarized, and a patient will be counted once within each ATC category (anatomic or therapeutic) linked to the medication. Therefore a patient may be counted several times for the same medication.

Prior medications will be presented by anatomic and therapeutic categories and sorted by decreasing frequency of ATC based on the overall incidence across treatment groups. In case of equal frequency regarding ATCs (anatomic or therapeutic categories), alphabetical order will be used.

Concomitant and posttreatment medications will be tabulated by anatomic and therapeutic categories and sorted by decreasing frequency in the sotagliflozin group. In case of equal frequency regarding ATCs (anatomic or therapeutic categories), alphabetical order will be used.

Prior and concomitant medications will also be presented for the ABPM substudy population for each treatment group, using counts and percentages.

